3.2.1. Inclusion Criteria

All of the criteria listed below must be met in order for an individual to be included in this study.

- At least 15 years of age or older
- Willing and able to provide informed consent for participation in this study
- HIV-positive
- Have at least one sex partner in the catchment area with an unknown HIV status at the time of study enrollment (defined as never testing for HIV or testing HIV negative more than 6 months ago)
- No history of intimate partner violence in the past 12 months
- No fear of intimate partner violence as a consequence of participating in the study
- Not enrolled in the INTERVAL study (no co-enrollment)

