3.3.1. Description of Randomization and Study Arms

Randomization from Aim 1 will be accomplished such that facilities randomized to the self-test intervention in Aim 1 will be self-test intervention sites for Aim 2 and sites randomized to standard of care and optimized standard of care for Aim 1 will continue as standard of care and optimized standard of care sites for Aim 2.

Description of Study Arms

1. **Standard of care arm:** Facilities randomized to the standard of care arm will use MOH approved referral mechanisms, without any intervention from the study team. Standard of care quality will vary by facility and may include some level of partner referral services for index partners such as referral slips. Referral slips may be given at HIV testing or ART clinics. Sites will be asked to counsel clients to have their partners bring referral slips back to the clinic to document the number of partners presenting for HIV testing. A random subset of HIV-positive clients in the standard of care arm will complete an anonymous survey to answer questions about whether they used referral slips and whether they know if partners came to a health facility for testing.

2. **Optimized standard of care arm:** Facilities randomized to optimized standard of care will be supported by the study team to systematically perform referral services following Ministry of Health Guidelines. Providers will receive an initial refresher training on partner testing followed by regular mentoring visits. Job aids will also be used to remind providers about the importance of partner testing. Standard of care procedures involve counseling HIV-positive individuals about the importance of partner testing and providing ‘referral slips’ to the index client to distribute to every sexual partner within the prior 12 months. Referral slips will be used to encourage partners to come to the facility for HIV testing. Sites will be asked to counsel clients to have their partners bring referral slips back to the clinic to document the number of partners presenting for HIV testing. A random subset of participants in the optimized standard of care arm will complete an anonymous survey to answer questions about whether they used referral slips and whether they know if partners came to a health facility for testing.

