4.3. Partner Self-Testing Arm

3.4.4.1 Baseline Visit for Index Client

A random sample of individuals will be screened and consented as they exit their ART visit. This will include ART clients who report having a sexual partner with an unknown HIV status. After written informed consent has been obtained, study staff will collect basic socio-demographics (including age, gender, marital status, and number of partners), HIV characteristics (date of HIV diagnosis, whether on ART and date started), and the number of eligible sexual partners they plan to give self-test kits.

The study staff will counsel the index client on how to administer an HIV self-test and will provide one self-test kit for each sexual partner within the last 12 months with unknown status (or HIV-negative more than 6 months ago) who lives within the catchment area of the facility and for whom the index client is willing to provide the test kit (up to three sexual partners). Index clients will also be given self-test kits for themselves if they wish to use them to complete couples counseling. All HIV self-test kits will be labeled with a unique ID linked to the index client participant. The ID will also be used to link index client survey responses with returned self-test kits.

The number of partners and the number of kits provided will be documented by study staff. Each self-test kit will be in a package that also contains a referral card. The referral card can be used for (1) those who test HIV-positive and need to present for confirmatory testing and link to care, (2) those who do not want to use the self-test kit and would rather test with an HDA, or (3) clients who experience difficulty or discomfort with the self-test kit and choose to test at a facility. The referral card will include information about the fa-

cility, including a map. The card will also contain a notation that if it is returned to another facility, the facility should contact the study team so that the card can be collected and recorded as “returned”. Study staff will periodically visit nearby testing sites to determine if any referral cards have been returned to those sites.

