5. STATISTICAL METHODS

5.1. Outcome Measures

3.5.1.1 Sample Size and Statistical Analysis for Primary Outcome Measures

We will have 15 clusters (facilities) available for randomization, and therefore, estimated our sample size assuming a fixed number of clusters (k) and an equal number of clusters per arm. We also assumed an equal number of participants per cluster. The below calculations were determined using a minimum sample size. Assuming a type I error of 0.05, an intracluster correlation of 0.004 and sample sizes of 600 HIV-positive patients per arm, we have 89% power to detect a difference in testing coverage of 20% in study arm 2 (optimized standard of care) and 40% in study arm 3 (self-testing). Because we are uncertain about the proportion of partners who will test under each arm, we have considered a range of possibilities, with the majority of scenarios providing at least 87% power to detect a difference between the two arms of interest (optimized standard of care and self-testing) (Figure 4).

We will calculate descriptive statistics, including mean/median, variation (standard deviation, kurtosis), range, and frequency distributions for the demographic and clinical characteristics, overall and by study arm. The outcomes of interest include the proportion of partners tested and HIV-positivity of partners. Differences in the prevalence of each of the outcomes of interest will be examined by study arm as well as by other factors of interest including demographic characteristics (e.g., age, gender), clinical characteristics (e.g., reason for clinic visit), and structural factors (e.g., geographic location). The differences will be evaluated using t-tests, Mann-Whitney U test (or other non-parametric tests), chi-square methods, and Fisher's exact test as appropriate. In order to assess factors associated with partner's HIV testing/positivity, we will use hierarchical linear models in order to account for clustering of effects within each clinic. Separate models will be developed for each outcome of interest and covariates of interest include patient characteristics (e.g., age, gender) and other structural and contextual factors.

Qualitative Analysis for Secondary Outcome Measures

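### The Aim 2 factor analysis models partner-level outcomes with the clinic as its only clustering level; if partners are the records, standard errors for index-client characteristics are too small

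*Combined protocol and SAP*

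**What the plan says.** For Aim 2, section 3.5.1.1 defines the outcomes at partner level: "The outcomes of interest include the proportion of partners tested and HIV-positivity of partners". For factors associated with those outcomes, it says "we will use hierarchical linear models in order to account for clustering of effects within each clinic", with a separate model for each outcome; "covariates of interest include patient characteristics (e.g., age, gender) and other structural and contextual factors". The clinic is the only level named. The sample size in the same section counts index clients: "sample sizes of 600 HIV-positive patients per arm".

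Elsewhere the plan allows several partners per client:

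- **Eligibility (3.2.1):** one partner is the minimum, not the limit: "Have at least one sex partner in the catchment area with an unknown HIV status at the time of study enrollment".
- **Self-test arm (3.4.4.1):** one kit is supplied for each recent partner of unknown status in the catchment area "for whom the index client is willing to provide the test kit (up to three sexual partners".
- **Optimized standard of care arm (3.3.1):** referral slips go "to the index client to distribute to every sexual partner within the prior 12 months", with no cap stated.

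In the self-test arm the client can be identified from a returned kit: "All HIV self-test kits will be labeled with a unique ID linked to the index client participant". Section 3.4.4.3 describes a similar code on the referral cards. In the two standard of care arms there are no kits, and the register data are anonymized. No section provides an index-client random effect, a client-clustered variance or a rule of one partner per client.

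**The concern.** Partners are nested in index clients, and clients in facilities. Partners of one client have a reason to be alike: the same person decides whether to disclose and to pass on kits or slips, and at follow-up reports on all of them. Aim 1 uses almost the same model sentence (section 2.5.1), but there the outcome belongs to the client and this extra level does not exist.

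An index client's age or gender is constant across that client's partners. A model that knows only the clinic counts two or three correlated partner records as two or three independent pieces of evidence about that characteristic. At stake is the planned analysis of whose partners get tested or test positive. Its intervals would be too narrow and some associations would look firmer than they are. This matters for a protocol whose background section stresses that men are being missed.

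**Working it through.** **The plan's own figure.** The only related figure is the 89% power for 20% against 40% tested, which concerns the arm contrast. With 600 clients per arm in 5 facilities (120 each) and an intracluster correlation (ICC) of 0.004, the design effect is 1 + 119 × 0.004 = 1.476. The effective n is 600 / 1.476 = 406.5 per arm, and power exceeds 99.9%. The 89% does not reproduce. An ICC of 0.04 gives 1 + 119 × 0.04 = 5.76, an effective n of 104.2 and power of 88.9%. That mismatch is a separate matter; it is used below only to test the arm contrast.

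**Inputs for the client level.** From the documents: partner-level outcomes, clinic-only clustering, at least one partner per client, up to three in the self-test arm, and a type I error of 0.05 (two-sided assumed). Not in the documents, so assumed: the shares of clients with 1, 2 or 3 partners (m) and the within-client correlation (ρ).

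**Formulas.** For a factor that is constant within a client:

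- design effect D = 1 + (E[m²]/E[m] − 1) × ρ
- true standard error / clinic-only standard error = √D
- shortfall = 1 − 1/√D
- real type I error = 2 × [1 − Φ(1.96/√D)]

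Example: for a 60/25/15% mix, E[m] = 0.60 + 0.50 + 0.45 = 1.55 and E[m²] = 0.60 + 1.00 + 1.35 = 2.95, so the ratio is 1.903. At ρ = 0.8, D = 1 + 0.903 × 0.8 = 1.72 and √D = 1.31.

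| Clients with 1/2/3 partners | E[m] | E[m²]/E[m] | ρ | D | Shortfall in SE | Real type I error |
|---|---|---|---|---|---|---|
| 90/8/2% | 1.12 | 1.25 | 0.3 | 1.08 | 3.6% | 5.9% |
| 90/8/2% | 1.12 | 1.25 | 0.8 | 1.20 | 8.7% | 7.4% |
| 80/15/5% | 1.25 | 1.48 | 0.3 | 1.14 | 6.5% | 6.7% |
| 80/15/5% | 1.25 | 1.48 | 0.8 | 1.38 | 15.0% | 9.6% |
| 60/25/15% | 1.55 | 1.90 | 0.3 | 1.27 | 11.3% | 8.2% |
| 60/25/15% | 1.55 | 1.90 | 0.8 | 1.72 | 23.8% | 13.5% |

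If every client has one partner, D = 1 and nothing is lost.

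**Check by simulation.** A linear mixed model with a facility intercept only was fitted to 10 facilities of 120 clients, with no true effects.

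- With 3,000 runs per case and the three mixes above, standard errors for a client-level factor were about 3% to 24% too small. Type I error was 5.7% to 13%, against 5.4% with one partner each.
- A second simulation used 400 runs per case and set ρ on a latent scale, so the correlation of the binary outcomes was lower. At a mean of 1.12 partners and ρ = 0.3 it found no understatement (empirical over model standard error 0.98; type I error 4.8%). At a mean of 1.5 (60/30/10%) and ρ = 0.8 it found 1.25 and 12.5%.

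**The arm contrast.** Arm varies between facilities, so the facility effect already carries most of the extra variance. In the second simulation, the ratio for arm was 0.95 to 1.04 and the type I error on 8 degrees of freedom was 2.3% to 3.8%.

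Power tells the same story. Take N = 600 × E[m] partners per arm and D = 1 + (E[m²]/E[m] − 1)(ρ − ICC) + (N/5 − 1) × ICC. At ICC 0.04, mean 1.55 and ρ = 0.8, D = 1 + 0.903 × 0.76 + 185 × 0.04 = 9.09, the effective n is 930 / 9.09 = 102, and power is 88.3%. Across the six cases it is 88.3% to 89.9%, against 88.9% with one partner each. At ICC 0.004 power stays above 99.9%.

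**The case against.** The strongest reply is that the plan never makes the partner the analysis record. It counts index clients in the sample size and lists t-tests and linear models, which would also fit one record per client, namely the share of that client's partners tested. On that reading clients nest in clinics and the problem disappears. This stands, so the point is conditional. It does not remove the point, because the outcomes and the model target are worded at partner level and nothing states the alternative.

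The size is also wholly assumed. Partners given kits must be of unknown status, recent, in the catchment area and acceptable to the client, so 40% of clients with two or three may be too many, and the low end of the range is negligible. This stands too. Nor do the documents show that one client's decision settles the outcome for all partners: section 3.4.4.1 makes willingness specific to each partner. Some positive correlation is plausible, but its strength is unknown.

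A reader might infer that the cap of three and the linked kit IDs hold in every arm. They belong to the self-test arm only. A reader might also infer that the Aim 2 primary comparison is compromised. The arm results above do not support that.

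**Conclusion.** The point holds in a limited, conditional form. If partners are the records in the Aim 2 factor analysis and the covariates are the index client's, clinic-only clustering understates their standard errors. Under the assumed partner mixes and correlations the understatement is about 4% to 24%, with a real type I error of about 6% to 13.5% by formula. The upper end needs 40% of clients with two or three partners together with a correlation of 0.8. The documents cannot place the trial within that range.

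It would go too far to say that the standard errors are too small as a matter of fact, since the unit is unstated, or that the randomized comparison of self-testing with optimized standard of care is at risk. This is a small to moderate point about a supporting analysis, worth correcting because the correction is cheap.

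**What to change.** In section 3.5.1.1 for Aim 2, state the analysis unit.

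- **If it is the partner:** add an index-client level within facility for both partner testing and partner positivity. A client-clustered variance alongside the facility effect is a lighter alternative.
- **If it is the client:** analyse testing as k partners tested out of m eligible partners listed at baseline, with one record per client. This covers testing only, so positivity needs its own statement.
- **In either case:** state where client-linked counts come from. The self-test arm has client-linked kit and card codes as well as surveys. In the standard and optimized arms the counts must come from the baseline and follow-up surveys, because register data are anonymized.

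The cost is a few sentences and one variance term; no new data are needed, since the surveys already ask for partner numbers and testing. Intervals for client-level factors will be slightly wider. If most clients have one partner, the client variance will be weakly identified, which favours the clustered variance or the one-record analysis.

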6. COST AND COST-EFFECTIVENESS METHODS

It is expected that partner self-testing will be cost-effective compared to optimized standard of care. For facilities, fewer HDA visits by patients should save the time of HDA staff. Partner self-testing may also lead to an increase in HIV-positive individuals identified because clients may be more comfortable doing the test in a private place. The study will estimate differences in overall costs for both optimized standard of care and partner self-testing. The average cost per successful outcome (index partner completes an HIV test) will be calculated.

Using the average cost per patient as described above, we will then estimate the cost for each newly identified HIV-positive partner. We will compare average cost per HIV-positive individual identified between study arms. To provide information for HIV program budgets, we will also estimate the annual cost of providing HIV testing under the two main strategies being evaluated (optimized standard of care and self-testing), independent of outcomes.

6.1. Costs to Provider

Costs will be measured from the provider perspective. We will use micro-costing methods to estimate the cost of HIV testing in all three study arms.^{25, 26, 27} We will first create an inventory of all the resources used to achieve the observed study outcomes. Resources to be captured will include:

- HIV self-test kits
- Standard of care HIV testing supplies
- Other services provided (e.g. counseling interactions)
- Fixed costs of patient care (building space, equipment, human resources)

For each study patient, the quantity (number of units) of resources used will be determined. Unit costs of resources, which are not human subjects data, will be obtained from external suppliers and the site's finance and procurement records and multiplied by the resource usage data to provide an average cost per study patient across centers in each study arm. Costs will be reported as means (standard deviations) and medians (IQRs) in USD, using the exchange rate prevailing during the follow up period.

6.2. Cost-Effectiveness

Using the average cost per patient as described above, we will then estimate the cost per outcome achieved in each arm. The main measure of effectiveness for the cost-effectiveness analysis will be both the primary study outcome of proportion of partners tested as well as yield (newly identified HIV-positive partners of index cases). We will calculate the difference in cost divided by the difference in effectiveness among study arms for both effectiveness measures.

The price of the self-test itself is currently uncertain because it is not widely available in Malawi. As such, we will conduct a sensitivity analysis where all costs and outcomes remain constant, and the price of self-tests alone is varied. This analysis will then provide a plausible range of the cost-effectiveness of partner self-testing.

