2.6. COST AND COST-EFFECTIVENESS METHODS

It is expected that group self-testing will be cost-effective compared to standard of care and optimized standard of care for HIV testing. For facilities, fewer HDA staff would be needed to achieve testing coverage, and it is possible that more positives will be identified. The study will estimate differences in overall costs for both standard of care arms and group self-testing. Costs of HIV testing will be estimated as the average cost per individual who completes an HIV test.

Using the average cost per patient tested we will estimate the cost for identifying each HIV-positive individual. We will compare average cost per HIV-positive individual identified among the three study arms with the primary comparison of optimized standard of care compared to group self-testing. To provide information for HIV program budgets, we will also estimate the annual cost of providing HIV testing at a site under the three strategies evaluated, independent of outcomes.

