2.6.2. Cost-Effectiveness

Using the average cost per patient as described above, we will then estimate the cost per outcome achieved in each arm. Two measures of effectiveness will be utilized for the cost-effectiveness analysis: the proportion of individuals tested for HIV and the cost per HIV-positive individual identified. We will calculate the difference in cost divided by the difference in effectiveness between study arms for both measures of effectiveness.

The price of the self-test (if self-testing were to become widely available in Malawi) is currently uncertain. As such, we will conduct a sensitivity analysis where all costs and outcomes remain constant, and the price of self-tests alone is varied. This analysis will then provide a plausible range of the cost-effectiveness of self-testing.

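### The cost-effectiveness ratios, a primary objective in both aims, do not tie the cost unit to the effect unit

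*Combined protocol and SAP*

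**What the plan says.** Cost-effectiveness against optimized standard of care is a primary objective of both aims (sections 2.1.1 and 3.1.1).

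**Aim 2.** Section 6.1 multiplies resource use by unit cost "to provide an average cost per study patient across centers in each study arm". Section 6.2 carries this forward as an average cost per patient and names as effectiveness "both the primary study outcome of proportion of partners tested as well as yield", yield being newly identified HIV-positive partners. It then states: "We will calculate the difference in cost divided by the difference in effectiveness among study arms for both effectiveness measures". The opening of section 6 mentions two other costs: "The study will estimate differences in overall costs for both optimized standard of care and partner self-testing", and "The average cost per successful outcome (index partner completes an HIV test) will be calculated". Study patient is not defined. The people enrolled are HIV-positive index clients with at least one partner of unknown status (section 3.2.1), and in the self-testing arm each may receive kits for up to three partners (section 4.3, under 3.4.4.1).

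**Aim 1.** Section 2.6 says: "Costs of HIV testing will be estimated as the average cost per individual who completes an HIV test". Section 2.6.1 instead ends in a cost per study patient, tested or not. Section 2.6.2 says: "Using the average cost per patient as described above, we will then estimate the cost per outcome achieved in each arm", without saying which of the two it means. Its first effect is the share of individuals tested. Its second is the cost of finding one HIV-positive person, which is itself a cost.

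**The concern.** An incremental cost-effectiveness ratio can be interpreted only if cost and effect are counted over the same unit. If cost is per index client and effect is per partner, the result is neither the cost per additional partner tested nor the cost per additional client reached. If cost is per completed test, it has already been divided by the effect, and dividing again by the difference in coverage can make a strategy that raises total spending look free or cost-saving. If the effect is itself a cost, the ratio has no meaning as a price per unit of benefit.

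At stake is a primary result in each aim. Two analysts could each follow a sentence of the plan and report different ratios.

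**Working it through.** The plan states no cost, no cost-effectiveness ratio and no mean number of partners, so there is no economic figure to reproduce. The check is of units, using the plan's coverage assumptions.

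**Aim 2: inputs**
- p2 = 0.20 (optimized standard of care) and p3 = 0.40 (self-testing), from 3.5.1.1, taken here as shares of partners.
- C2, C3: mean cost per index client, the natural reading of 6.1.
- m2, m3: mean eligible partners per index client. These are not stated. Eligibility requires at least 1, and kits are capped at 3 in the self-testing arm. All values below are assumptions.

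**Aim 2: formulas**
- Ratio as read literally: (C3 − C2)/(p3 − p2).
- Cost per additional partner tested: (C3 − C2)/(m3·p3 − m2·p2).
- Literal divided by consistent: (m3·p3 − m2·p2)/(p3 − p2). At 0.20 and 0.40 this is (0.40·m3 − 0.20·m2)/0.20 = 2·m3 − m2.

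With m equal in both arms the factor is m. For an assumed cost difference of $5 per client, the literal ratio is 5/0.20 = $25:

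| m (both arms) | Consistent ratio, 5/(0.20·m) | Factor |
|---|---|---|
| 1 | $25.00 | 1.00 |
| 1.1 | $22.73 | 1.10 |
| 1.25 | $20.00 | 1.25 |
| 1.5 | $16.67 | 1.50 |
| 2 | $12.50 | 2.00 |
| 3 | $8.33 | 3.00 |

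With m unequal the factor is not the mean of the two:

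| m2 | m3 | Factor, 2·m3 − m2 | Mean of m |
|---|---|---|---|
| 1.0 | 1.1 | 1.20 | 1.05 |
| 1.1 | 1.2 | 1.30 | 1.15 |
| 1.2 | 1.1 | 1.00 | 1.15 |
| 1.5 | 1.2 | 0.90 | 1.35 |
| 1.2 | 1.5 | 1.80 | 1.35 |

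**Aim 2: the other costs in section 6**
- Cost per completed partner test. If this is c in both arms, the ratio is (c − c)/0.20 = 0. On a per-eligible-partner basis it is (0.40c − 0.20c)/0.20 = c.
- Overall cost. An arm total depends on how many clients the arm holds, so dividing a difference in totals by a difference in proportions does not give a cost per partner either.
- Two pairings do match: cost and effect both per eligible partner, or both per index client. Neither is stated.

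**Aim 2: yield.** Section 6.2 gives this measure no denominator. If it is counted per index client, it matches a cost per index client and there is no distortion.

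**Aim 1: inputs.** Coverage of 10% in arm 2 and 60% in arm 3 (section 2.5.1), a difference of 0.50. Costs are assumed.

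| Assumed costs | Per-completed-test basis (2.6) | Per-attender basis (2.6.1) |
|---|---|---|
| Completed test costs c in both arms | (c − c)/0.50 = 0 | (0.60c − 0.10c)/0.50 = c |
| Completed self-test costs 0.8c, standard test c | (0.8c − c)/0.50 = −0.4c | (0.60 × 0.8c − 0.10c)/0.50 = +0.76c |
| $1 (arm 2) and $4 (arm 3) per attender | 1/0.10 = $10.00 and 4/0.60 = $6.67; (6.67 − 10.00)/0.50 = −$6.67 | (4 − 1)/0.50 = +$6.00 |

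In the last two rows the choice of unit alone reverses the sign.

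**Aim 1: second measure.** Section 2.6.2 lists the cost of finding one HIV-positive person as a measure of effectiveness and then divides a difference in cost by a difference in effectiveness. That divides a cost by a cost.

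**The case against.** The best defence is that the unit is left open rather than wrongly chosen. Nowhere does the plan say cost per index client. In Aim 2 the word patient is used loosely: 3.5.1.1 uses it for the HIV-positive people sampled, while the follow-up sections sometimes use it for a partner who starts ART. Section 6.1 speaks of resources used to achieve the study outcomes, which are partner tests, and sections 6 and 6.2 also plan a cost per outcome. Section 3.5.1.1 applies 20% and 40% to 600 HIV-positive patients per arm, so the coverage denominator is itself unclear; if coverage were per index client, the units would agree. In Aim 1, the nearest antecedent of section 2.6.2 is the per-study-patient cost of 2.6.1, which is the suitable basis.

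Much of this stands, and it limits what can be claimed about size. It does not rescue the ratio. The per-outcome costs are average ratios within an arm, whereas 6.2 separately asks for a difference over a difference. Sections 5.1 and 6.2 both name the share of partners as the outcome, and none of the costs stated for Aim 2 is said to be per partner eligible for testing.

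A reader might go further and infer that the Aim 2 result is wrong by the mean number of partners per client, perhaps threefold. The documents do not support that. They give no mean; the limit of three is a cap on kits, not an average; and the factor equals m only when m is the same in both arms. Nor do they show that the Aim 1 ratio will have the wrong sign. That happens only if the cost in section 2.6 is used.

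**Conclusion.** The point holds as a mismatch, or failure to match, of units in a primary-objective analysis. Its size cannot be fixed from the documents.

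- **Aim 2, partners tested.** Reading study patient as the enrolled index client, the ratio is not the cost per additional partner tested. The factor is 2·m3 − m2 at the planned coverage. It is 1 with one partner per client, equals m when m is equal across arms, and was 0.90 to 1.80 in the unequal examples. This assumes that 20% and 40% are shares of partners.
- **Aim 2, yield.** No denominator is stated, so this ratio may be unaffected.
- **Aim 1, share tested.** The nearer reading is sound. The alternative in section 2.6 could reverse the sign, and the text does not exclude it.
- **Aim 1, second measure.** A cost is named as an effect. This does not depend on how study patient is read.

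**What to change.** In Aim 2 section 6.2, define the incremental ratio as the difference in mean cost per index client, including the cost of testing that client's partners, divided by (a) the difference in partners tested per index client and (b) the difference in newly identified HIV-positive partners per index client. In 6.1, say that study patient means the index client. Effects counted per client need no partner denominator, so differences between arms in the number of eligible partners no longer distort the ratio.

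In section 2.6.2, use the difference in mean cost per eligible attender, tested or not, divided by (a) the difference in the proportion of attenders tested and (b) the difference in HIV-positive people identified per attender. Measure (b) replaces the cost now listed as an effect.

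Keep cost per completed test and cost per HIV-positive person found as descriptive averages by arm, outside the incremental ratios.

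The cost is a few sentences settled before analysis. Enrolment, randomization and data collection do not change: eligible partners are recorded at baseline in every arm, and the follow-up survey already asks index clients in every arm whether partners tested and with what result.
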